#### **4.4.1.3 Severity of Adverse Event**

A summary of TEAEs by primary SOC, preferred term, and severity will be presented in two tables. The first table will present mild/moderate TEAEs and the second table will present severe and potentially life threatening TEAEs. Subjects will be classified for each preferred term under the maximum severity experienced and summarized on the appropriate table. That is to say, if a subject experiences the same AE with a moderate and severe grade the subject will be counted on the second table and not the first.

#### **4.4.1.4 Serious Adverse Events**

Summary tables of serious AEs (SAEs) and related SAEs by primary SOC and preferred term by treatment arm will be provided. Furthermore, a summary of serious TEAEs leading to death will be presented.

All SAE data will be presented in a by-subject listing.

#### **4.4.1.5 Premature Discontinuations Due to Adverse Events**

Summary tables of AEs leading to study drug discontinuation by primary SOC and preferred term by treatment arm will be provided. Adverse events leading to study drug discontinuation will be listed by subject.

#### **4.4.2 Clinical Laboratory Result Analysis**

The safety labs include the following tests:

- Serum Chemistry: Na, K, Cl, bicarbonate, glucose, Ca, BUN, Creatinine, ALT, AST, Alkaline Phosphatase, total bilirubin (Central lab)
- Complete Blood Count with differential (Hemoglobin, Hematocrit, and WBC with differential count) (Local lab)
- Pregnancy test: Serum or Urine hCG (Local lab)
- Antibodies to ART-123 (Central lab)

If a lab value is reported using a non-numeric qualifier (eg, less than (<) a certain value, or greater than (>) a certain value), the given numeric value will be used in the summarization for >X and half the reported value used for <X.

Laboratory abnormalities will not be graded. All collected laboratory evaluations will be presented in by-subject data listings.

Baseline is defined as the last non-missing value before first dose.

Summary statistics for actual values and for changes from baseline will be tabulated for laboratory results by analysis visits as outlined in the analysis visit window structure found in [section 3.3](#) of this SAP. Change from baseline calculations will only be summarized for subjects with non-missing baseline and post baseline values. Subjects with clinical laboratory values outside of the normal reference range will be summarized by shift tables. Figures of the mean safety laboratory result over time will also be presented.

The above summaries will be performed for the complete blood count with differentials, serum chemistry, and for hematology labs.

A listing of collected labs and their associated normal ranges will also be presented for both the global central lab and local lab data.

Additionally, an extreme range shift table for baseline to post-baseline value at post-baseline analysis visits as described in [section 2.3](#) of the SAP will be presented by treatment arm on the safety population. The definition of extreme ranges for specified labs is given in [appendix B](#) of this SAP.

#### 4.4.3 Antibody Analysis (Anti-drug antibody to ART-123)

Anti-drug antibodies to ART-123 will be evaluated and presented in a listing. A summary of antibody analysis results will be presented by treatment group, overall, and for each visit. This summary table will include the number of screening assays analyzed and the number and percent of subjects having positive and negative results from the analyzed assay including the screening and confirmatory assay. All collected antibody data will be presented in a by subject listing. Titer and Neutralizing antibody results will only be available for subjects with confirmed positive ADA results.

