- Anti-drug antibodies to ART-123. Additionally, all subjects that develop anti-drug antibodies to ART-123 will be followed for blood draw and medical evaluation at 3 months intervals until their serum antibody titer results become negative for a maximum duration of 18 months. Serum samples from subjects that have demonstrated the development of antidrug antibodies that are present on Day 28 or End of Study Visit will be tested for the presence of neutralizing antibodies.

Note: Survival status for all subjects must be reflective of survival status on calendar Day 29.

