7.6.3 Laboratory Sample Categories

There are four types of clinical laboratory evaluations: Safety, Coagulation Panel, Organ Dysfunction, and Exploratory.

Safety laboratory tests include the following:

- Serum Chemistry: Chemistry (Na, K, Cl, Bicarbonate, Glucose, Ca, BUN, Creatinine, ALT, AST, Alkaline Phosphatase, Total bilirubin)
- Complete Blood Count with differential (RBC, Hemoglobin, Hematocrit, and WBC with differential count)
- Pregnancy test: Serum or Urine hCG
- Platelet count
- Antibodies to ART-123.

Note: All subjects that develop positive antibodies to ART-123 at Day 28 will be followed at 3 month intervals until their serum antibody titer level returns back to baseline or for a maximum of 18 months.

Coagulation Panel includes the following tests:

- Prothrombin time

- INR
- D-dimer

Organ Dysfunction labs include the following tests:

- Serum creatinine
- Total bilirubin
- PaO₂/FiO₂ ratio

Exploratory labs include the following tests:

- Coagulation: functional protein C, TAT, F1.2, PAI-1 and ATIII
- Inflammation: CRP, Microparticles, and C5a
- Plasma thrombomodulin concentration (PK)
- Arterial lactate concentration

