#### **Secondary:**

- Assessment of the efficacy of ART-123 in resolution of organ dysfunction in this population.
- Assessment of antidrug antibody development in subjects with coagulopathy due to bacterial infection treated with ART-123.

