### **2.5 Blinding**

Study drug is supplied as individual glass ampules containing blinded study drug (ART-123 or placebo). Study drug will be assigned and administered in a double blinded fashion, both the subject and the study site will be blinded as to the subject randomization.

In addition, Asahi Kasei Pharma America Corporation and the CRO's supporting the study will be blinded with the following exceptions:

- 1) The DMC will be unblinded. If the DMC believes it is imperative to unblind Asahi Kasei Pharma America Corporation the process and procedures outlined in the DMC charter will be followed.
- 2) The independent statistician supporting the DMC will be unblinded.
- 3) Designated personnel from the CRO supporting safety event reporting will be responsible for unblinding the safety events for regulatory reporting.

- 4) Although all site personnel are to be blinded, if it is medically imperative for the Investigator or authorized person to be unblinded they are to contact the Medical Monitor or designee to discuss the rationale for unblinding. The Investigator must document the rationale for and all activities associated with the unblinding and follow all procedures for reporting and recording of unblinding.
- 5) Drug supply and accountability services will be unblinded.
- 6) Central laboratory and exploratory laboratories, who handle pharmacokinetics data and biomarker data, will be unblinded.
- 7) Should a subject be ART-123 antibody positive the site will be required to follow the subject for antibody status. Not all subjects with a positive result on the assay will have taken ART-123. Designated personnel from the CRO supporting safety event reporting will be responsible for informing the sites of the need for additional follow-up.

Once the last subject has reached Day 28 and the appropriate data cleaning activities have taken place the clinical database through study day 28 will be locked and the sponsor will be unblinded. At this point follow-up to determine mortality status will continue. To limit potential bias study sites and study subjects will remain blinded to treatment assignment during this long-term follow-up.

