### Secondary Safety Endpoint

- Anti-ART 123 antibodies

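### SAP 4.4.3 pre-specifies only visit-by-visit antibody positivity, so the secondary objective of antibody development has no pre-specified per-subject treatment-emergent incidence

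*SAP*

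**What the plan says.** SAP 1.1 gives as a secondary objective: "Assessment of antidrug antibody development in subjects with coagulopathy due to bacterial infection treated with ART-123". SAP 3.2 carries this as the only secondary safety endpoint, "Anti-ART 123 antibodies", with no further definition.

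The analysis is in SAP 4.4.3: "A summary of antibody analysis results will be presented by treatment group, overall, and for each visit". The statistics are the number of screening assays analysed and "the number and percent of subjects having positive and negative results from the analyzed assay including the screening and confirmatory assay". At subject level, "All collected antibody data will be presented in a by subject listing".

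The protocol draws antibody samples at baseline before dosing (5.3), Day 14 (5.12), hospital discharge (5.14) and Day 28 (5.15), and every 3 months in subjects with a positive result (5.18). SAP 4.4.3 makes a titre available for confirmed positives. SAP 2.5 notes that "Not all subjects with a positive result on the assay will have taken ART-123".

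On how long positive subjects are followed, Protocol 5.15 says "until their serum antibody titer results become negative for a maximum duration of 18 months", while Protocol 7.6.3 says "until their serum antibody titer level returns back to baseline or for a maximum of 18 months".

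**The concern.** Development is a change within a subject: not positive before dosing and positive after, or a higher titre after than before. A percentage positive at each visit is a prevalence. It mixes subjects who were already reactive with those who became so, and its denominator is whoever is alive and sampled at that visit. It also does not show whether a subject positive at Day 14 is the same subject who is positive at Day 28. Followed as written, the plan gives a set of marginal percentages from which the number of subjects who developed antibodies cannot be read.

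The definition could be supplied later from the listings. But the titre-rise threshold, the denominator and the handling of unmapped samples would then be chosen after unblinding.

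**Working it through.** **1. Figure to reproduce.** There is none. The documents give no antibody rate, precision or sample-size statement.

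**2. Is the gap filled elsewhere?** SAP 4.4.2 lists antibodies among the safety laboratory tests, but limits its change-from-baseline and shift summaries to blood count, chemistry and hematology. SAP 4.4.1 defines treatment-emergent for adverse events only. SAP Appendix B has no antibody row. SAP 4.4.4 does plan a baseline shift table for ECG, so the device is used in this SAP, but not for antibodies.

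**3. Windowing.** SAP 4.1 remaps all visits through 28 days to Table 1 and presents summaries on that basis. Table 1 has no discharge visit. Day 14 takes Study Days 10–18 (192 to under 408 hours) and Day 28 takes Study Days 24–32 (552 to under 744 hours). Since 408 = 17 × 24 and 552 = 23 × 24, Study Days 19–23 fall between the windows by either clock. SAP 3.3 says unmapped records are listed but left out of by-visit tables. A subject positive only at a discharge draw on those days therefore appears in no row.

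**4. Changing denominators.** Under Protocol 10.1 (24% vs 16% mortality, 800 subjects randomised 1:1, so about 400 per arm), deaths by Day 28 would be 400 × 0.24 = 96 on placebo and 400 × 0.16 = 64 on ART-123. That leaves 304 and 336 subjects. Protocol 5.15 also allows the Day 28 visit by telephone, without blood draws. The baseline and Day 28 rows thus describe different sets of subjects.

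**5. Size at one visit (all rates assumed).** Let b = share positive at baseline, r = share of those still positive at the visit, e = incidence among baseline-negative subjects. With everyone sampled:

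- percent positive at the visit = b·r + (1 − b)·e
- excess over incidence = b·(r − e)

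With e = 3%:

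| b | r = 1 | r = 0.5 |
|---|---|---|
| 0% | 3.00% | 3.00% |
| 1% | 3.97% | 3.47% |
| 2% | 4.94% | 3.94% |
| 5% | 7.85% | 5.35% |
| 10% | 12.70% | 7.70% |

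At b = 5% and r = 1, 400 × 0.0785 = 31.4 subjects count as positive, of whom 400 × 0.95 × 0.03 = 11.4 are treatment-emergent. Over b = 0–10%, e = 1–5% and r = 0.5–1, the excess runs from 0 (b = 0) to 0.10 × (1 − 0.01) = 9.9 points.

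The error can also go the other way. If 3% are positive at Day 14 and 3% at Day 28, with none positive at baseline, the share ever positive lies anywhere from 3% (same subjects) to 6% (different subjects).

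**6. Arm difference.** With equal b and r in both arms and no induced antibodies on placebo, the difference is (1 − b)·e. At b = 5%, e = 3%, r = 1 this is 7.85% − 5.00% = 2.85 points, close to the assumed 3%.

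**7. Follow-up passages side by side.**

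| Protocol place | Who is followed | Until |
|---|---|---|
| 5.15; 5.19 Table 1, footnote 10 | subjects who develop antibodies | negative |
| 5.18; 7.2 | any subject with a positive result | negative |
| 7.6.3 | subjects who develop positive antibodies at Day 28 | titre back to baseline |

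All are capped at 18 months. A subject positive at baseline and unchanged enters under 5.18 and 7.2, but not clearly under 5.15. A subject whose titre has returned to a positive baseline has finished under 7.6.3 but not under 5.18. Under 5.18 and 7.2 the same rule governs how long serious and thrombotic events are collected.

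**The case against.** **The table allows for much of this.** It has a baseline row, a Day 14 row and a placebo column, and nothing singles out Day 28. Pre-existing reactivity is balanced in expectation by randomisation, and step 6 shows that it nearly cancels in the arm difference. This stands, and it rules out the reading that the arm comparison is badly distorted. It does not supply a count of subjects who converted, and the balance holds at randomisation rather than among survivors with a sample.

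**Baseline positivity may be negligible.** Exclusion 8 bars previous ART-123 treatment, and the sentence in SAP 2.5 says only that a positive result does not prove exposure. It does not say that positives are expected before dosing. This also stands, and the excess at a single visit may be zero. The changing denominators, the uncounted ever-positives and the unmapped discharge samples remain even then.

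**The discharge loss is narrow.** A subject discharged on Study Days 19–23 was due a Day 14 draw and must return for Day 28. Only positivity seen at discharge alone, or followed by a missed Day 28 draw, is lost. The loss also depends on the SAP 4.1 remapping applying to SAP 4.4.3, which names visits without saying which kind.

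**Two stronger readings are tempting.** A reader might infer that treatment-emergent incidence cannot be obtained. It can: the samples are taken and every result is listed. A reader might also infer that SAP 4.4.3 promises neutralising tests for all confirmed positives, against Protocol 5.15 and 5.18, which test antibodies present at Day 28 or End of Study. The SAP says only that such results will not exist for anyone else, so there is no conflict.

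**Conclusion.** The point holds as a gap in pre-specification. A stated secondary objective has no planned analysis that answers it per subject, although the data to do so are collected. The effect on a single-visit percentage is unknown, because no rates are given; the range of 0 to 9.9 points rests entirely on the assumed prevalence, incidence and persistence. The endpoint is descriptive, no safety testing is planned (SAP 3.7), and the mortality analysis is untouched. This is a cheap improvement rather than a threat to the trial. The differing follow-up passages are a separate inconsistency that can be seen from the text alone.

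**What to change.** In SAP 4.4.3, add one per-subject table by actual treatment in the safety population, giving the number and percent of subjects who are either:

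- negative at baseline and confirmed positive at any post-dose sample (Day 14, discharge or Day 28), whatever the analysis-visit window; or
- positive at baseline with a titre rise of at least a pre-specified size.

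The denominator is subjects with a baseline and at least one post-dose sample. Show baseline-positive subjects separately, and keep the by-visit table as it is.

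The cost is one extra table and a titre-rise threshold that must be fixed before unblinding. The samples and titres are already planned.

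Separately, reconcile Protocol 5.15, 5.18, 5.19 (Table 1, footnote 10), 7.2 and 7.6.3 on a single trigger and a single end rule for following positive subjects. This review does not say which rule is right. The change alters subject visits and the period of event collection, so it needs a written amendment under Protocol 8.1.

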#### 4.4.4 ECG

Subject’s ECGs will be read centrally and the final read/interpretation of the ECG will be forwarded to the sites. ECG results, including general findings, heart rate (beats/minute), and PR, QRS, and QTc intervals (seconds) will be available. A change from baseline summary table will be presented. Also, a shift from baseline table by normal/abnormal flag, as defined [Table 2](#) will be presented for all scheduled post dose visits and will display the number and percent of subjects for each shift.

**Table 2: ECG Normal Range**

Interval	Normal	Abnormal, Clinically Insignificant	Abnormal, Potentially Clinically Significant
HR	50-100 bpm	40 - < 50 or > 100 – 150 bpm	< 40 or > 150 bpm
PR	120 – 220 msec	< 120 or > 220 – 240 msec	> 240 msec
QRS	≤ 110 msec	111 - 120 msec	> 120 msec
QTcB (QTcF)	Female: ≤ 470 msec Male: ≤ 450 msec	Female: > 471 - 500 msec Male: >451 - 500 msec	Female: > 500 msec Male: > 500 msec

The observed data at baseline and change from baseline for each scheduled post dose visits will be summarized with descriptive statistics. Change from baseline will only be calculated for subject having non-missing baseline and post baseline measurements. The number of subjects with a QTc result > 500 msec or a change from baseline > 30 msec or > 60 msec will be summarized at each visit. A by-subject listing of ECG recordings will also be provided. All summaries presented will be by actual treatment group.

ECG data will be presented in a by subject listing.

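### SAP Table 2 leaves a 1 msec gap between normal and abnormal QTc (451 msec in men, 471 msec in women), so the ECG shift table has no defined category for those readings

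*SAP*

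**What the plan says.** SAP Table 2 sorts each ECG interval into three columns: normal; abnormal but clinically insignificant; and abnormal and potentially clinically significant. The QTcB (QTcF) row reads:

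- Normal: "Female: ≤ 470 msec Male: ≤ 450 msec"
- Abnormal, insignificant: "Female: > 471 - 500 msec Male: >451 - 500 msec"
- Abnormal, potentially significant: "Female: > 500 msec Male: > 500 msec"

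SAP Section 4.4.4 makes the table operative. It plans "a shift from baseline table by normal/abnormal flag, as defined" in Table 2, for every scheduled post-dose visit, with the number and percent of subjects in each shift. The same section describes the intervals in seconds ("QRS, and QTc intervals (seconds) will be available"), while Table 2 works in milliseconds. Neither place states how many decimals are recorded.

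Separately from the categories, the text below Table 2 plans a summary at each visit of "The number of subjects with a QTc result > 500 msec or a change from baseline > 30 msec or > 60 msec".

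**The concern.** Categories that define a flag should cover every possible value exactly once. Here the upper limit of normal and the lower limit of the next column differ by 1 msec, and the second limit is strict. A reading of exactly 451 msec in a man is not normal, because it exceeds 450. It is not in the middle column, because it does not exceed 451. It is not in the top column, because it does not exceed 500. The same holds for 471 msec in a woman.

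A shift cell needs both the baseline and the post-dose reading to be classified, so one orphaned reading is enough to leave a pair undefined. Protocol Table 1 schedules the central ECG at baseline, Day 3, Day 6, Day 7, early treatment termination, Day 14 and hospital discharge, so the flag is applied repeatedly. The SAP has no rule for an unmatched value, and its general conventions (Section 4.1) take all subjects in the treatment group as the default denominator. Whether such a subject is shown as missing, left out of the cells but kept in the denominator, or placed in a column by the programmer is not pre-specified.

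**Working it through.** **1. Coverage of the categories.** Inputs are the limits in SAP Table 2. Each whole-millisecond QTc value from 300 to 650 was tested against the three columns, by sex.

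| Sex | Normal | Middle column as printed | Top | Values with no category |
|---|---|---|---|---|
| Women | ≤ 470 | > 471 to 500 | > 500 | 471 |
| Men | ≤ 450 | > 451 to 500 | > 500 | 451 |

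No value fell in two columns. For readings with fractions of a millisecond, the gap is the interval above 470 up to and including 471 (women) and above 450 up to and including 451 (men).

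**2. The other rows.** The same test found no uncovered whole value for HR (50–100, then 40 to < 50 or > 100 to 150, then beyond), PR (120–220, then < 120 or > 220 to 240, then > 240) or QRS (≤ 110, then 111–120, then > 120). HR and PR use a strict sign with the same number as the normal limit. QRS uses the next whole number without a strict sign. The QTc row combines the strict sign with the next whole number, and that combination produces the gap.

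**3. After correction.** With the middle column starting above 470 (women) and above 450 (men), every whole value from 300 to 650 falls in exactly one column.

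**4. Possible size.** The plan states no figure on this point, so there is nothing to reproduce. It also gives no QTc mean, SD or sex mix. The following are assumptions: normal distribution, the same mean and SD in both sexes, mean 410–470 msec, SD 20–50 msec, 50% or 60% men, readings recorded to the whole millisecond.

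- Men: p_M = P(450.5 < QTc < 451.5)
- Women: p_W = P(470.5 < QTc < 471.5)
- All readings: p = m × p_M + (1 − m) × p_W, where m is the share of men

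| Mean, SD (msec) | m | p_M | p_W | p |
|---|---|---|---|---|
| 440, 30 | 0.6 | 1.24% | 0.78% | 0.6 × 1.24 + 0.4 × 0.78 = 1.06% |
| 410, 20 (lowest in grid) | 0.5 | 0.24% | 0.02% | 0.5 × 0.24 + 0.5 × 0.02 = 0.13% |
| 460, 20 (highest in grid) | 0.6 | 1.80% | 1.71% | 0.6 × 1.80 + 0.4 × 1.71 = 1.76% (1.77% before rounding the inputs) |

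Over the whole grid p runs from 0.13% to 1.77%. In a narrower band (mean 420–460, SD 25–45) it runs from 0.47% to 1.48%.

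The share of baseline/post-dose pairs with at least one orphaned reading cannot exceed the sum of the two shares. At the top of the grid that is 2 × 1.77% = 3.54%. This bound does not require the two readings to be independent, which repeated readings in one subject are unlikely to be.

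**The case against.** The strongest reply is that the intention is plain. Section 4.4.4 speaks of a normal/abnormal flag, and 451 msec in a man is clearly not normal under Table 2, so a two-way flag would call it abnormal. The QRS row shows that the authors probably meant from 451 and from 471. This is a fair guess at the intent, but the section says the flag is defined by Table 2, and neither abnormal column contains the value. A programmer working from the three columns as printed has to improvise. A lost ≥ sign in the PDF conversion cannot be excluded entirely. However, ≤ survives in the same row and ≥ appears elsewhere in the SAP (Section 4.2.3), so the printed text is the one to work from.

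A second reply concerns precision. If QTc were stored in seconds to two decimals, as in the adult QTc row of the toxicity table in Protocol Appendix I, neither 0.451 nor 0.471 could occur. That stands, because the recording precision is not given. With fractional milliseconds, on the other hand, the QRS row would also have a gap, above 110 and below 111. The statement that only the QTc row fails therefore holds for whole units only.

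A third reply is that little depends on this table, and that also stands. SAP Section 3.7 plans no safety testing. Clinically significant ECG changes are assessed by the investigator and recorded as adverse events (Protocol Section 7.8). The protocol's own QTcB thresholds (Sections 2.7.1 and 5.8) are 500 msec and 60 msec over baseline, not 450 or 470. The gap applies in the same way to both arms, and nothing in the documents points to a bias between them.

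A reader might infer that about 1% of ECGs drop out of the shift table, or that new QTc prolongations are lost. The documents support neither. They contain no QTc distribution from which 1% could be derived, and they do not say that unmatched values are dropped.

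**Conclusion.** Table 2 is wrong as written. One whole-millisecond value per sex has no category, in a table that defines the flag for a planned output. This is a faulty boundary in an analysis rule; no calculation in the plan is in error.

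The impact is very small. It reaches only a descriptive shift table, at the border between normal and a column already labelled clinically insignificant. Prolongations remain visible in the counts of QTc above 500 msec, the counts of changes above 30 and 60 msec, the descriptive statistics of values and changes, and the by-subject listings. Efficacy analyses are not touched.

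The existence of the gap follows from the printed limits alone. The size, roughly 0.1% to 1.8% of readings, rests entirely on the assumed distribution and on whole-millisecond recording, and should be read only as an order of magnitude.

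**What to change.** In SAP Table 2, change the middle cell of the QTcB (QTcF) row to: Female: > 470 - 500 msec; Male: > 450 - 500 msec. The normal limits and the limit of 500 msec stay as they are, and no clinical rule in the protocol changes. The cost is one table cell, best corrected before the shift table is programmed.
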